## PROTOCOL SUMMARY

TITLE OF THE STUDY: Prediction of Itraconazole Oral Absorption From In Vitro Dissolution

PHASE: Phase 4

METHODOLOGY: Randomized, open-label, 4-way, cross-over, four period, fasted single-dose study comparing pharmacokinetic area-under-the-curve (AUC) of fast tablet, medium tablet, and slow tablet.

STUDY CENTER: University of Maryland

NUMBER OF SUBJECTS: at least n=12

STUDY OBJECTIVES: The primary outcome will be the assessment of pharmacokinetic area-under-the-curve (AUC) of fast tablet, medium tablet, and slow tablet, with regard to rank-order of point estimates, after a single oral dose of itraconazole in at least n=12 healthy volunteers. It is hypothesized that fast dissolving tablet will provide the highest AUC point estimate value, and the slow dissolving tablet will provide the lowest AUC point estimate value.

## Prediction of Itraconazole Oral Absorption From In Vitro Dissolution

### Lay Summary

For tablets to be absorbed, the drug must dissolve after being swallowed. Drugs with low solubility sometimes require the inert ingredients in tablets to help the drug dissolve after being swallowed. This study uses itraconazole as an example drug with low solubility. Itraconazole tablets with different inert ingredients and manufacturing will be administered to healthy volunteers to see if the different inert ingredients and manufacturing impact drug absorption.

### Background

Itraconazole is an example drug with low solubility, where the rate of drug dissolution will impact the amount of drug that is absorbed. A measure of the amount of drug that is absorbed is pharmacokinetic area-under-the-curve (AUC). It is hypothesized that fast dissolving tablet will provide the highest AUC point estimate value, and the slow dissolving tablet will provide the lowest AUC point estimate value.

### Procedures

In this non-treatment, pharmacokinetic study. There will be a screening visit and four pharmacokinetic study arms for all enrolled subjects. Subjects will be enrolled on an ongoing basis until either the anticipated number of required subjects for at least n=12 completed subjects is achieved. In each pharmacokinetic study visit occasion, individual subjects will receive a single dose of one (and only one) of four drug products. The products are fast tablet, medium tablet, slow tablet, and commercial oral solution.

Subjects will be randomized into one of four sequences, A, B, C, or D. Sequence A will receive drug products in the following order: 1, 2, 4, 3. Sequence B will receive drug products in the following order: 2, 3, 1, 4. Sequence C will receive drug products in the following order: 3, 4, 2, 1. Sequence D will receive drug products in the following order: 4, 1, 3, 2. Numbers 1, 2, 3, 4, are Fast tablet, Medium tablet, Slow tablet, and oral solution, respectively.

Each tablet contains itraconazole 100mg, which is sub-clinical in amount. The dose of commercial oral solution (10mg/ml) is also itraconazole 100mg. In each period, blood samples will be collected 0-48 h. Additionally, for oral solution, a blood samples will be collected at 72.0 hr post-dose.

Screening: At this visit, the HIPAA and consent forms will be reviewed with the subject by a member of the research staff; they will be signed and dated. Consenting will also discuss and provide a payment plan. Demographic information will be obtained. A brief physical exam with a medical/medication history, including smoking and alcohol, will be conducted. ECG will be performed. Clinical safety labs at screening include hepatic and renal function tests (i.e. creatinine, AST, ALT, and total bilirubin), and hemoglobin to test for anemia. Female subjects will be asked if they are breast feeding, trying to become pregnant, or are pregnant. Female subjects of child-bearing potential will have a urine pregnancy test. The subject will be asked about willingness to avoid caffeine products for 24 hours before and day of study visit. The subject will be asked about willingness to stop Over-the-Counter (OTC) drugs for 24 hours before and days of study visits. The subject will be asked if willing, for each of the four drug study periods, to stop consuming grapefruit, grapefruit products, star fruit, star fruit products, Seville oranges, or St. John's wort from 72-hour before study drug administration until the period's last blood sample. The subject will be asked if willing to fast during the study visits except for meals supplied in the study. If subject meets all eligibility requirements, then appointments are scheduled for the drug study visits. The first study visit will be within 30 days of the screening visit.

Drug/Pharmacokinetic Study Visits: Subjects will be requested to arrive by approximately 7am on study visit, after an overnight fast of 10 hours prior to taking test drug, and remain fasted for an additional 4 hours. Women of child-bearing potential will take a urine pregnancy test.

Drug (i.e. a single tablet or 10ml of oral solution) will be orally administered with 240ml of clear, non-bottled water at approximately 8am. All drugs will be stored and dispensed by the UMMC investigational drug pharmacy. Pharmacokinetic (PK) blood levels will be drawn at the schedule times: prior to drug administration, then after drug administration at 1.0, 2.0, 3.0, 4.0, 5.0, 6.0, 8.0, 12.0, 15.0, 24.0, 36.0, and 48.0 hr post-dose. Additionally, for oral solution, a blood samples will be collected at 72.0 hr post-dose.

Standardized meals and snacks will be served during each PK study arm. Meals and snacks include beverages. Four hours after taking test drug, or approximately noon, a lunch will be served. Lunch beverage will only include clear, non-bottled water. Lunch will exclude beverage with low pH (e.g. soft drinks, fruit juices, sport and energy drinks, tea, coffee). An afternoon snack will be served 3 hours later, or at approximately 3pm. Dinner will be served 3 hours later or at approximately 6pm. An evening snack will be served 3 hours later, or at approximately

9pm. While in the GCRC, subjects will fast between meals or snacks except for clear, non-bottled water. However, no water is allowed 1 hour before and after drug administration. There are 4 visits for each tablet arm (i.e. a second, third, and fourth visit of the arm for the 24, 36, and 48 hr blood draws, respectively). There are 5 visits for the oral solution arm (i.e. a second, third, fourth, and fifth visit of the arm for the 24, 36, 48, and 72 hr blood draws, respectively). Subjects will return for the next study arm, preferably 1 week later with a minimum of a wash out of 7 days and no more than 60 days.

Subjects will be monitored for AEs during study days. At each study visit, subjects will be asked about any AE that may have occurred between study visits. At the last study visit, an additional 5 cc (1 teaspoon) will be collected for liver function test safety labs. All AE will be documented in the source documents by research personnel. AEs and SAEs will be reported per UMB HRPO guidelines.

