## Monitoring Plan

Data Safety Monitoring will be performed by a physician who is not on the study team. In closed review of subjects (i.e. de-identified data), the physician will review the following information: AEs (recorded on a flow sheet), screen failures, subject withdraws and terminations, and enrollment. Reviewed data will include clinical summaries, enrollment numbers, and adverse events. Additionally, she will conduct such reviews after the completion of the first four subjects, and then quarterly.

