## Statistical Analysis Plan

This is a pharmacokinetic, in vitro-in vivo correlation study. The primary outcome will be the assessment of pharmacokinetic area-under-the-curve (AUC) of fast tablet, medium tablet, and slow tablet, with regard to rank-order of point estimates, after a single oral dose of itraconazole in at least n=12 healthy volunteers. It is hypothesized that fast dissolving tablet will provide the highest AUC point estimate value, and the slow dissolving tablet will provide the lowest AUC point estimate value. The point estimate is the simple mean value. There will either be a rank-order correlation or not.

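### Can the tablet ranking be trusted when the plan does not say whose AUCs enter the three means?

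*Combined protocol and SAP*

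**What the plan says.** Three places give the sample size. The Protocol Summary has "NUMBER OF SUBJECTS: at least n=12". The Statistical Analysis Plan places the primary comparison "after a single oral dose of itraconazole in at least n=12 healthy volunteers". Procedures is more specific: "Subjects will be enrolled on an ongoing basis until either the anticipated number of required subjects for at least n=12 completed subjects is achieved". That sentence has an unmatched either and refers to an anticipated number that is not given.

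On the analysis, the Statistical Analysis Plan says "The point estimate is the simple mean value" and, for the outcome, "There will either be a rank-order correlation or not". Only the three tablets are ranked; the oral solution is given but not ranked. No analysis set is named, and there is no rule for a subject who misses a period.

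Withdrawals appear once, in the Monitoring Plan, among the items for the safety physician: "screen failures, subject withdraws and terminations, and enrollment". Periods are separated "with a minimum of a wash out of 7 days and no more than 60 days".

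**The concern.** In a crossover each subject should contribute to every product mean, so that differences between subjects cancel. A subject who leaves early may contribute to one or two tablets only. If such AUCs are kept, the three means rest on different people and between-subject variation enters the ranking.

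Withdrawal is plausible. A completer attends 3 × 4 + 5 = 17 study visits after screening, and the first and last doses are 3 × 7 = 21 to 3 × 60 = 180 days apart.

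The word completed is also open at the edges. "Sequence B will receive drug products in the following order: 2, 3, 1, 4": a subject in that sequence who leaves before period 4 has all three tablet AUCs but has not finished the study.

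The primary result is a bare yes or no, without a test or margin. If two readings of the plan gave opposite answers, the choice between them could be made after the AUCs were known.

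**Working it through.** **The plan's own figure.** The 12 cannot be reproduced. The documents give no expected difference, variability, error rate or dropout rate, so what follows rests on assumptions.

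**Can the answer flip?** Yes. Suppose 12 completers have mean AUCs of 1000, 900 and 800 (fast, medium, slow): the answer is yes. Add one withdrawal with only a fast AUC of 350 and another with only a medium AUC of 1600:

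- fast: (12 × 1000 + 350) / 13 = 950.0
- medium: (12 × 900 + 1600) / 13 = 953.8
- slow: 800

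The answer becomes no.

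**How often?** Inputs from the protocol: the four sequences, the floor of 12 completers, and the rule that a yes needs mean fast > medium > slow. Assumed: lognormal AUC; between/within-subject CV of 40%/30% or 60%/40%; an AUC ratio per step of 1.0, 0.9, 0.8 or 0.7; and 1, 2 or 4 withdrawals leaving at random after period 1, 2 or 3, unrelated to AUC. There were 20,000 runs per cell.

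Completers-only and all-available means disagreed in 6.0-12.5% of trials (ratio 1.0), 8.4-19.3% (0.9), 3.3-13.5% (0.8) and 0.3-4.2% (0.7).

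**Is that due to the unnamed analysis set?** For comparison, the extra subjects were made full completers, so that every mean used the same people. The table uses CVs of 40%/30%.

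| Ratio per step | Extra subjects | Extras withdraw: completers vs all available differ | Extras complete: first 12 vs all differ | Completers vs all-three-tablet set differ |
|---|---|---|---|---|
| 1.0 | 2 | 9.5% | 10.3% | 1.2% |
| 1.0 | 4 | 12.4% | 13.6% | 2.3% |
| 0.9 | 2 | 13.4% | 15.1% | 1.8% |
| 0.9 | 4 | 18.8% | 21.0% | 3.3% |
| 0.8 | 2 | 4.8% | 5.0% | 0.5% |
| 0.8 | 4 | 6.7% | 6.5% | 1.1% |

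The simulation standard error for a rate near 15% is √(0.15 × 0.85 / 20,000) = 0.25 percentage points. Perfectly matched extra subjects therefore change the answer about as often as withdrawals do, and mostly slightly more often. Most of the instability comes from ranking three close means with no margin.

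**Does either reading favour a yes?** At ratio 0.9 with two withdrawals the chance of a yes is 59.2% for completers and 59.3% for all available. The largest gap in these runs is 60.1 − 59.3 = 0.8 points (ratio 0.9, four withdrawals). A wider set of assumed CVs gave at most about 2 points.

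**The Sequence B case.** Completers and subjects with all three tablets disagreed in 0.0-3.3% of runs. Sequence B is the only sequence with the solution last, so the two sets seldom differ.

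**Timing.** Subjects still in the study when the twelfth finishes become completers if they continue, and so enter both means. The 21 to 180 days therefore contribute nothing to the disagreement rates.

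**The case for a change.** The best case for a change is that a recruitment target is not an analysis set. The Statistical Analysis Plan does not use the word completed, and with a yes/no outcome nothing else in the plan limits the choice. At a 10% step with two withdrawals, the two readings part in about one trial in seven (13.4%). A sentence would cost nothing and would preserve the within-subject comparison.

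Two parts of this stand. The text does not name the set, and all-available means do give up some of the crossover's matching. That loss would grow if between-subject variation were far larger than within-subject variation, because matched means are much less exposed to it.

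The rest does not carry a change. One sentence on the analysis set would leave the ranking about as fragile as before, since matched extra subjects move it as much. Going further would add little. Replacing withdrawals in the same sequence is a preference, as no sequence imbalance has been shown and no period effect was simulated. A log-scale mixed model as a sensitivity analysis would change the estimator along with the subjects, so a different ranking could not be put down to the analysis set.

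**Conclusion.** No change is needed. The omission is real, but it is missing detail rather than a rule that produces a wrong result. Read together, the three sample-size statements point to completers, and an analyst of a four-period crossover would take the means over the same people without being told. If nobody withdraws, the readings coincide. If one to four subjects do, they disagree in between 0.3% and 19.3% of simulated trials, depending on how far apart the tablets are, with no material shift in the chance of a yes. The nearest alternative set differs from completers in at most 3.3%. The unfinished either is clerical.

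These sizes rest on assumed CVs, steps and withdrawal counts, and on withdrawal unrelated to AUC; withdrawal that depends on exposure was not simulated. The protocol describes the dose as sub-clinical and the subjects are healthy volunteers, so such a link is not an obvious worry. The fragility of a ranking without a margin is a separate matter, which naming the analysis set would not settle.

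### Equal sequence numbers among analysed subjects are not guaranteed, so any period effect adds noise to the unadjusted tablet means that are ranked

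*Combined protocol and SAP*

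**What the plan says.** The Protocol Summary describes the trial as a "Randomized, open-label, 4-way, cross-over, four period, fasted single-dose study". Procedures gives the allocation in one sentence, "Subjects will be randomized into one of four sequences, A, B, C, or D". With the products coded 1 = fast, 2 = medium, 3 = slow and 4 = oral solution, the orders are 1-2-4-3 for A, 2-3-1-4 for B, 3-4-2-1 for C and 4-1-3-2 for D.

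No allocation ratio, block size, quota per sequence or replacement rule is given. Enrolment runs "until either the anticipated number of required subjects for at least n=12 completed subjects is achieved", which is a total across sequences and need not be a multiple of four.

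The Statistical Analysis Plan makes the order of the three tablet AUC estimates the whole primary result, read as present or absent. It fixes the estimator: "The point estimate is the simple mean value". It names no period, sequence or subject term, no analysis set and no handling of partial data.

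**The concern.** A Williams square is chosen so that each product is taken equally often in each period and follows every other product equally often. With simple means, that protection holds only if the sequences contribute equal numbers to the analysis. Here the stopping rule counts completers in total, and the estimator cannot correct an unequal split afterwards. If AUC shifts between periods, an unequal split moves the tablet means relative to one another.

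The primary result is an order of three numbers with no interval or test. If a shift swapped two adjacent tablets, nothing in the planned output would show it. Separately, if AUCs from subjects who leave early were averaged in, the three means would rest on partly different subjects, and between-subject differences would enter a comparison that the crossover is meant to keep within subject.

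**Working it through.** The plan gives no alpha, power, effect size or SD, so the figure of 12 cannot be re-derived. The check concerns balance only. From the documents: the four orders, the total of at least 12 completers, and the simple mean. Assumed: drift per period, within- and between-subject CV, spacing of the tablets, and dropout.

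**1. The square.** Period in which each tablet is taken:

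| Sequence | Fast | Medium | Slow |
|---|---|---|---|
| A | 1 | 2 | 4 |
| B | 3 | 1 | 2 |
| C | 4 | 3 | 1 |
| D | 2 | 4 | 3 |

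Each column sums to 10, so with equal numbers every tablet has mean period 2.5. All 12 ordered product pairs occur once. The square is correct.

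**2. Effect of an unequal split.** Shift in a difference of means = drift per period × difference in mean period, where mean period = Σ(n_s × period)/n.

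For A/B/C/D = 4/3/3/2:
- fast: (4 + 9 + 12 + 4)/12 = 29/12
- medium: (8 + 3 + 9 + 8)/12 = 28/12
- slow: (16 + 6 + 3 + 6)/12 = 31/12

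At an assumed drift of +10% of the mean per period, in percentage points:

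| Split | Fast − medium | Medium − slow | Fast − slow |
|---|---|---|---|
| 3/3/3/3 | 0 | 0 | 0 |
| 4/3/3/2 | +0.8 | −2.5 | −1.7 |
| 5/3/3/1 | +1.7 | −5.0 | −3.3 |
| 4/3/3/3 (n = 13) | −0.8 | −1.5 | −2.3 |

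At 5% drift these halve. At zero drift they vanish.

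**3. If randomization were simple (not stated).**
- P(3/3/3/3) = 12!/[(3!)⁴ × 4¹²] = 0.022.
- Some sequence is empty in 12.5% of trials. The largest and smallest differ by 3 or more in 70.5%.
- Fast-minus-slow period differences for A to D are −3, +1, +3, −1. Their mean is 0 and their SD is √(20/4) = 2.236, so the SD of the net imbalance is 2.236/√12 = 0.645 period.
- For adjacent tablets it is √(10/4)/√12 = 0.456 period.

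The mean of 0 shows that no tablet is favoured on average.

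**4. If the list were in blocks of four**, with the next subject on the list replacing each dropout until 12 complete (simulation):
- Exact 3/3/3/3 survives in 42% of trials at 10% total dropout and in 21% at 20%.
- At 5% dropout per period, the fast-minus-slow imbalance SD is 0.29 period, and a difference of 3 or more between sequences occurs in 7%.
- At 10% per period these are 0.37 period and 20%.

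**5. Chance of the correct order** (simulation; within-subject CV 30%, between-subject CV 50%, adjacent ratios 1.15, 12 completers):

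| Drift per period | Equal split | Simple randomization | SD of log(fast/slow), equal to simple |
|---|---|---|---|
| 5% | 70.4% | 70.1% | not computed |
| 10% | 70% | 68% | 0.138 to 0.151 |
| 15% | 69% | 65% | 0.142 to 0.168 |

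With no drift there is no loss. With a blocked list, 10% drift and 5% dropout per period, the figures are 69.9% for equal split against 69.7%. Over drifts of 0 to 15% and about 15% total dropout, the loss with a blocked list is about 0 to 1 point.

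Other assumptions change the size. With tablets 10% apart, within-subject CV 20% and 10% drift, an equal split gives 72%, simple randomization 68% and a fixed 5/3/3/1 split 62%. At CV 40%, equal and simple give 45% and 44%.

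**6. If partial data were averaged.**
- With 10% dropout per period, within-subject CV 30% and between-subject CV 80%, the SD of log(fast/slow) rises from 0.148 to 0.167 and the correct order falls from 67% to 64%.
- With tablets 10% apart, CVs of 20% and 50%, no drift and 8% dropout before each later period, it falls from 74% to 66%. That run did not replace dropouts, so part of its loss is simply fewer observations.

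**The case against.** The strongest reply is that Procedures is silent on the list, and silence is not a rule. A reader might infer from the allocation sentence that randomization is unrestricted and that balance therefore has a 2.2% chance. The documents do not support that: a blocked list may exist unpublished, and the figures in step 3 hold only if it does not. This stands.

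The effect is also small. Drifts of 10% and 15% per period compound to 1.1³ = 1.33 and 1.15³ = 1.52 from period 1 to period 4, and must be common to all subjects. Nothing in the documents points to such drift. One week between arms is preferred although up to 60 days is allowed; fasting, dosing time, water and meals are standardized; and ongoing enrolment staggers calendar time across subjects. Within-subject variability matters more to the order than imbalance does. All of this stands, and it limits the size.

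Finally, an analysis of completers is a natural reading of the enrolment target. In that analysis each subject contributes to all three means and between-subject differences cancel. That is fair: the partial-data problem is conditional on an analysis set that the plan leaves undefined.

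The reply does not remove two stated features. Closure on a total permits unequal sequences, and 13 or 14 completers cannot be split equally. The simple mean has no means of adjusting for it. Nor does a blocked list settle the matter, since step 4 shows exact balance usually lost at modest dropout. Each subject has 4 + 4 + 4 + 5 = 17 visits, so some dropout is plausible.

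**Conclusion.** The point holds in a limited form. The stopping rule and the estimator together leave the square's protection against period effects unsecured among analysed subjects, and whether the list is blocked is unknown.

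A reader might infer that the ranking is biased towards one tablet. It is not: under simple randomization the shift averages zero. It is extra noise, which becomes a fixed error in whichever split is realised, and it is zero without a period effect.

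At CVs of 30% and 50% and adjacent ratios of 1.15, the chance of the correct order falls by about 2 points (10% drift) or 4 to 5 points (15%) under simple randomization, and by about 1 point or less with a blocked list and ordinary dropout. The documents give none of these variabilities, drifts or dropout rates, so the sizes are illustrative. Between-subject differences add to this only if partial data are averaged. The loss is modest. The case for acting is that the balance was designed in and costs very little to keep.

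**What to change.** In Procedures:
- Randomize in permuted blocks of four, each containing A, B, C and D once.
- Assign each replacement to the sequence of the subject replaced.
- Close enrolment when every sequence has the same number of subjects with all three tablet AUCs: three each, or another multiple of four in total.

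In the Statistical Analysis Plan:
- Compute the three tablet means on that same set.
- If the analysed sequences still end up unequal, take the point estimates from a model with subject, period and product terms, which removes an additive period effect at any split.

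The set counted for closure must be the set analysed. Sequence B takes the oral solution last. If closure counted four-period completers but the means used everyone with three tablet AUCs, a sequence B subject lost before the last period would be both analysed and replaced, and sequence B would be over-filled. The text should therefore also say what counts as a completed subject.

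Cost: a new list, a few sentences and possibly one or two extra replacements. A replacement's sequence is known in advance, which matters little because the study is already open-label and AUC comes from measured blood levels.

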#### EXCLUSION CRITERIA:

1. Subject has a significant medical disease (including cardiovascular, pulmonary, hematologic, endocrine, immunologic, neurologic, gastrointestinal or psychiatric).
2. Subject shows evidence of congestive heart failure or history of congestive heart failure.
3. Subject exhibits electrocardiogram (12 lead) with clinically significant abnormalities (e.g. QTcF >450 msec).

4. Subject has a history of alcohol or drug abuse, which in the opinion of the investigator, could jeopardize the subject's health or would compromise the subject's ability to participate in this trial.
5. Subject is pregnant, breast feeding, or trying to become pregnant.
6. Female subject of childbearing potential is unwilling or unable to use a medically acceptable method of contraception throughout the entire study period and for one week after the study is completed. Medically acceptable methods of contraception that may be used by the subject and/or her partner are: oral birth control pill, condom with spermicide, diaphragm with spermicide, IUD, vaginal spermicidal suppository, surgical sterilization of patient or their partner(s), abstinence, or hormonal-based patches, ring, injections, and implants.
7. Subject routinely uses (i.e. daily or weekly) prescription medication except hormonal birth control medication, routinely uses (i.e. daily or weekly) OTC medication, or routinely uses (i.e. daily or weekly) St. John's Wort. OTC medications do not include vitamins, dietary supplements, or herbals.
8. Subject routinely uses (i.e. daily or weekly) acid blockers, antacids, anti-diarrhea, stimulants, appetite suppressants, or anti-nausea medication or other drugs that modulate GI function.
9. Subject is currently taking itraconazole or medication known to interact with itraconazole.
10. Subject is allergic to itraconazole.
11. Subject has liver impairment as assessed by alanine aminotransferase (ALT), aspartate aminotransferase (AST), or total bilirubin levels greater than the upper limit of normal (ULN).
12. Subject has renal impairment as assessed by creatinine clearance lower than 50mL/min/1.73m^2, using the CKD-EPI formula.
13. Subject is not willing or able to be adherent to study protocol (e.g. study visits).
14. Subject has a condition in which in the opinion of the PI or medical physician would increase risk to the subject or interfere with the integrity of the study.

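### After the fourth dose the last described adverse-event question comes at 48 h or 72 h, whereas doses 1 to 3 get a further question about 7 days or more after the dose

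*Combined protocol and SAP*

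**What the plan says.** All of this is in the Procedures section of the combined protocol and SAP.

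- **How AEs are found.** There are two mechanisms. One is observation: "Subjects will be monitored for AEs during study days". The other is questioning: "At each study visit, subjects will be asked about any AE that may have occurred between study visits".
- **Visits.** "There are 4 visits for each tablet arm", the last of them for the 48 h draw. The oral solution arm has a fifth visit, for the 72 h draw.
- **Spacing.** The next arm follows preferably a week later, "with a minimum of a wash out of 7 days and no more than 60 days".
- **Order of products.** Each of the four sequences ends with a different product. Only one ends with the solution (product 4): "Sequence B will receive drug products in the following order: 2, 3, 1, 4".
- **End of study.** "At the last study visit, an additional 5 cc (1 teaspoon) will be collected for liver function test safety labs". No exit visit, telephone call or other later contact is described.

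**The concern.** A question about the time between visits works only if another visit follows. It picks up late events after the first three doses because the subject comes back for the next arm. After the fourth dose nobody comes back, so the same mechanism stops at the final blood draw.

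The four doses all contain 100 mg of itraconazole. The length of AE questioning after a dose therefore depends on its place in the sequence, not on anything about the dose. At stake is the record of AEs that begin more than 2 or 3 days after the final dose. No described contact would elicit them.

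**Working it through.** The plan states no figure on this point, so there is none to reproduce. The check maps the last product in each sequence to the last visit of its arm and compares the follow-up with that after doses 1 to 3.

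**Inputs from Procedures.** Product codes are 1 fast tablet, 2 medium tablet, 3 slow tablet, 4 oral solution. Sequence orders are A 1-2-4-3, B 2-3-1-4, C 3-4-2-1 and D 4-1-3-2. The last draw is at 48 h (day 2) for tablets and 72 h (day 3) for the solution. The washout is at least 7 days.

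**Assumptions.** There are 12 completers, the stated minimum, with 3 per sequence. The window after each dose is W days; the protocol sets no W.

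**Step 1: number of visits.** 3 tablet arms × 4 + 1 solution arm × 5 = 17 pharmacokinetic visits per subject. Questioning within each arm is therefore frequent. The 17th visit is the last draw of the fourth arm.

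**Step 2: last question after doses 1 to 3.** This comes at the first visit of the next arm. If the washout runs from the dose, that is day 7 or later. If it runs from the last draw, it is day 2 + 7 = 9 or later (tablet), or day 3 + 7 = 10 or later (solution). Under either reading a 7-day window is covered.

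**Step 3: last question after dose 4, and days left uncovered when W = 7.**

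| Sequence | Fourth product | Last question | Uncovered days per subject | × 3 subjects |
|---|---|---|---|---|
| A | slow tablet | day 2 | 7 − 2 = 5 | 15 |
| B | oral solution | day 3 | 7 − 3 = 4 | 12 |
| C | fast tablet | day 2 | 5 | 15 |
| D | medium tablet | day 2 | 5 | 15 |

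Total: 15 + 12 + 15 + 15 = 57 dose-days.

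**Step 4: share.** Doses: 12 × 4 = 48, of which 12 (25%) are fourth doses. Dose-days: 48 × 7 = 336. Uncovered: 57 / 336 = 17.0%, all after dose 4.

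**Step 5: sensitivity.**

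- *Window.* For W = 2, the uncovered share is 0 of 48 × 2 = 96 (0%). For W = 3, it is 9 × 1 = 9 of 48 × 3 = 144 (6%). For W = 7, it is 17%.
- *Allocation.* With W = 7, each subject has 4 × 7 = 28 dose-days. The uncovered share is 5/28 = 18% for a tablet-last subject and 4/28 = 14% for a solution-last subject. Any split across sequences lies between these.

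**The case against.** The strongest reply is that the plan does what it sets out to do. It promises observation on study days and questions about the time between visits, and it delivers both. The question at day 7 or later after doses 1 to 3 is a by-product of a washout meant to separate periods, not a follow-up standard. The percentage depends on a window chosen for this check. The dose is described as sub-clinical, and subjects have had three earlier itraconazole doses with repeated questioning by then. The plan also says that all AEs will be documented, which is not limited to elicited ones. All of this stands. It makes the point a design choice with a better option, not a breach. It does not supply a contact after the last draw.

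Other parts of the plan do not supply one either. The independent physician under Monitoring Plan reviews recorded, de-identified data. The final liver test is drawn at the last visit and sees nothing later. The institutional guidelines are cited for reporting. They are outside the documents, and the consent pages were removed, so any instruction there cannot be checked.

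A reader might be tempted to infer more in three ways:

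- *That the protocol itself defines a post-study risk week.* Exclusion criterion 6 requires contraception "throughout the entire study period and for one week after the study is completed". It applies only to women of childbearing potential, whose number is not given. It is not tied to AEs, and it does not say that completion means the subject's own last visit. It cannot be turned into a period of missed follow-up for all subjects or used to set the date of a call.
- *That abnormal final liver results would not reach the subject.* The available text describes no such step, but the removed pages or external guidelines may cover it. The result can also be recorded without contact.
- *That a longer window would show a larger gap.* Beyond 7 days the answer depends on spacing between doses, which the plan leaves open between 7 and 60 days. The same calendar days can then fall after two doses. The documents support no single figure.

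**Conclusion.** The point holds as a low-weight gap in safety capture. As the plan is written, AE questioning ends 48 h after the fourth dose in sequences A, C and D and 72 h after it in sequence B. After each earlier dose a further question follows at about 7 days or later.

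The headline size, 17% of dose-days, rests on an assumed 7-day window, 12 completers and equal allocation. The fact that does not depend on the window is that every completer's final dose lacks the later question. The finding also assumes that the last study visit is the last draw of the fourth arm. The visit count and the description of the liver sample as additional both point that way.

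The shortfall does not fall on one product, because each product is last in exactly one sequence. Safety is not a stated objective, and the mean AUC values and their rank order do not depend on AE questioning.

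**What to change.** Add one sentence to the Drug/Pharmacokinetic Study Visits text under Procedures, for example: *Study staff will telephone each subject 7 to 10 days after the last dose received, including subjects who withdraw, to ask about any AE since the last visit.*

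The lower limit of 7 days matches the minimum that doses 1 to 3 already get. The upper limit is only a practical scheduling margin.

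The cost is about 12 short calls by existing staff, plus one for each withdrawn subject. Each completer's record closes later by 7 − 2 = 5 to 10 − 2 = 8 days when a tablet is last, and by 7 − 3 = 4 to 10 − 3 = 7 days when the solution is last. No visit or blood draw is added.
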